Aims 1 and 2 prospectively evaluate neuromuscular control among individuals with cerebral palsy who are receiving single-event multi-level orthopaedic surgery (SEMLS) as part of their standard care at Gillette Children's Specialty Healthcare. Our sample size analysis, based upon our prior analyses of synergy complexity repeatability and associations with outcomes, suggest a sample size of 55 subjects for 90% power to detect $\frac{1}{2}$ a standard deviation change in synergy complexity assuming a 20% drop-out rate, alpha = 0.05. This sample size is based upon Aim 2 to detect if synergies change after treatment. In our preliminary analysis, a $\frac{1}{2}$ standard deviation change in synergy complexity (Dynamic Motor Control, DMC) was associated with a 5-point difference in the Gait Deviation Index (GDI), which is generally the threshold for defining a clinically significant improvement in walking ability in clinical motion analysis. We are evaluating synergy complexity using DMC, which we previously evaluated and tested on over 500 children with cerebral palsy and 84 typically-developing children. In this prior research, DMC could differentiate between functional ability levels among individuals with cerebral palsy.

We use causal modeling and Bayesian Additive Regression Trees (Table 1) to evaluate whether pre-operative synergy complexity and structure are associated with changes in GDI after SEMLS at 12 months post-op. We constructed our causal model with a Directed Acyclic Graph (DAG). The logic behind our DAG is as follows:

1. Our objective was to determine the impact of SEMLS on change in GDI (Δ GDI). Thus, SEMLS is our exposure and Δ GDI is our outcome. SEMLS induces a change in impairments (Δ Imp) that causes the observed Δ GDI.
2. The covariates we identified as common causes of both SEMLS and Δ GDI included: Age, baseline GDI (GDI_{pre}), and baseline impairment (Imp_{pre}). Baseline impairments represent a set of variables collected during clinical gait analysis to evaluate neurologic and orthopedic impairments (Table 1).
3. Surgical treatment history (Hx) is a common cause of baseline impairment (Imp_{pre}) and whether or not SEMLS is recommended.
4. We included a general severity (Sev) measure as an unmeasured factor that impacts baseline impairment (Imp_{pre}) and surgical treatment history (Hx).

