From the DAG we determined the adjustment set needed (e.g., regression, BART) to evaluate the total causal effect of SEMLS on Δ GDI. For this DAG, the minimal sufficient adjustment set to estimate the total causal effect of SEMLS on Δ GDI was: Age, GDI_{pre} , and Imp_{pre} . We also determined the adjustment set to evaluate the total causal effect of baseline impairment (Imp_{pre}) on Δ GDI and GDI_{pre} . The minimal sufficient adjustments sets were Age and Hx for Δ GDI and Age for GDI_{pre} . The plausibility of a DAG can be evaluated by identifying conditional independencies, variables that should be independent given the causal relationships defined in the DAG. We identified the adjustment sets and independencies with dagitty⁴ and all analyses were conducted in R (version 4.1.0)⁵.

To assess the total causal effects of SEMLS and baseline impairments (Imp_{pre}) on change in GDI (Δ GDI) we used Bayesian Additive Regression Trees (BART), a machine learning method that uses a boosted ensemble of regression trees for nonparametric function estimation relying on a Bayesian probability model⁶. Like other tree-based regression methods, an advantage of BART is that it can handle nonlinear effects and interactions⁷. For causal modeling, recent work has demonstrated that BART-based models achieve accurate and precise causal predictions^{8,9}. For this analysis, we used BART models to estimate Δ GDI using the adjustment sets identified by the DAG. Thus, to identify the impact of SEMLS on Δ GDI, we included the covariates Age,

GDI_{pre} , and Imp_{pre} . Baseline impairments were not available for all participants. Missing data in Imp_{pre} were imputed using multivariate imputation by chained equations (MICE)¹⁰. We used the *bartMachine* package to implement the analysis¹¹. We optimized the hyperparameters for each BART model using 10-fold cross-validation. We report the pseudo- R^2 ($1 - \text{SSE}/\text{SST}$) for each BART model and used k-fold cross-validation ($k = 10$) to determine the out-of-sample root mean square error (RMSE).

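### The RMSE labelled out-of-sample comes from the children who also tuned the BART models, so unless tuning was nested it is expected to be modestly optimistic

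*Combined protocol and SAP*

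**What the plan says.** All the relevant text is in the Statistical Analysis section of the combined protocol and SAP, in the paragraphs on BART.

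- **Purpose of the models.** "To assess the total causal effects of SEMLS and baseline impairments" on change in GDI, the plan fits BART models with covariates taken from the DAG.
- **Missing data.** "Baseline impairments were not available for all participants", and the missing values "were imputed using multivariate imputation by chained equations (MICE" method). The plan does not give the amount missing, the variables in the imputation model, the number of imputations, or whether imputation was done before or within the folds.
- **Tuning.** "We optimized the hyperparameters for each BART model using 10-fold cross-validation". The hyperparameter grid and the fold handling are not given.
- **Error estimate.** The plan reports a pseudo-R-squared for each model. It then uses k-fold cross-validation, again with ten folds, "to determine the out-of-sample root mean square error (RMSE").

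No nesting of the tuning loop, separate test set or external sample is described. No RMSE value appears.

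**The concern.** Tuning is described per model, not per training fold, and the error estimate comes after it. The plain reading is that settings were chosen once, on all the children, and the tuned model was then cross-validated on those same children. Each held-out child has then already influenced the settings used to predict it. Such an error estimate is not out-of-sample with respect to tuning, and the expected direction is optimism.

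Aim 1 asks whether pre-operative synergies predict outcome at 12 months, and this RMSE is the only quantity in the plan labelled out-of-sample. The pseudo-R-squared is not described as cross-validated. A reader who wants to know how well the model would predict for a new child has only this figure.

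Imputation raises a second question of the same kind. If the imputation model was fitted to all children, and above all if it used their outcomes, held-out children would also inform the predictors used to judge them.

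**Working it through.** **1. What can be reproduced.** No RMSE is stated, so the figure at issue cannot be. The only reproducible design figure is "a sample size of 55 subjects for 90% power to detect" half a standard deviation of change, with 20% drop-out. For a paired t-test with d = 0.5, two-sided alpha 0.05 and power 0.90, the noncentral t gives n = 44 (power 0.9000), and 44 / (1 - 0.20) = 55. This matches. It sets a plausible range of 44-55 children, but the plan says the sample size was derived for Aim 2, not for BART.

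**2. Number of predictors.** From the adjustment set and Table 1: age, baseline GDI, four scores (spasticity, strength, static and dynamic motor control), two torsion measures and four contracture measures. That is 1 + 1 + 4 + 2 + 4 = 12, or 13 with the SEMLS indicator.

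**3. Tuning, simulation A.** Assumed: 13 correlated predictors, outcome SD about 10, kernel ridge regression in place of BART, and 18 settings. There were 60 runs per row at n = 44 and 55, and 6 at n = 200. Signal is the assumed R-squared. *Same folds* is the minimum cross-validated RMSE over the grid. *New folds* re-splits the children after tuning on all of them. *Fresh* is the error in 3,000 new subjects.

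| n | Signal | Same folds | New folds | Nested | Fresh | Same vs nested | New vs nested |
|---|---|---|---|---|---|---|---|
| 44 | 0.1 | 9.82 | 9.85 | 10.40 | 10.25 | -5.6% | -5.3% |
| 44 | 0.4 | 8.85 | 8.96 | 9.42 | 9.19 | -6.0% | -4.9% |
| 55 | 0.1 | 9.86 | 9.88 | 10.21 | 10.06 | -3.4% | -3.2% |
| 55 | 0.4 | 8.72 | 8.75 | 9.11 | 9.09 | -4.3% | -4.0% |
| 200 | 0.1 | 9.88 | 9.87 | 9.95 | 9.73 | -0.7% | -0.9% |
| 200 | 0.4 | 8.16 | 8.17 | 8.27 | 8.26 | -1.3% | -1.2% |

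Each percentage is 100 x (RMSE / nested RMSE - 1), for example 9.82 / 10.40 - 1 = -5.6%. New folds recover little, so the problem is reuse of the children, not of the fold labels. Against *fresh*, the same-fold gap at n = 44-55 is -4.2%, -3.7%, -2.0% and -4.1% (for example 9.82 / 10.25 - 1), because the nested estimate itself ran slightly high. With 6 runs, the n = 200 rows are too noisy for that comparison.

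**4. Tuning, simulations B and C.** Simulation B used a kernel proxy with 12 predictors, 18 settings, n = 44 and 120 runs at each of three signal strengths. Tuned RMSE against true RMSE was 0.986 / 1.033 (-4.5%), 1.025 / 1.077 (-4.8%) and 1.071 / 1.130 (-5.2%). Nested RMSE was 1.025, 1.079 and 1.126, all within 1% of the truth. Simulation C used a strongly regularised Gaussian-process stand-in at n = 44-55 and gave an RMSE only about 1-2% below nested.

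**5. Scale.** If a reader converts the RMSE to 1 - SSE/SST, a model with a true value of zero would show 1 - 0.99^2 = 0.02 at 1% optimism and 1 - 0.94^2 = 0.12 at 6%. In GDI points, assuming an RMSE of 8-12 (not in the documents), the range is 0.01 x 8 = 0.08 to 0.06 x 12 = 0.72 points. The plan's threshold for a clinically significant improvement is 5 points.

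**6. Imputation.** This was a separate simulation with regression imputation in place of MICE, fixed settings and signal 0.4. Imputing outside rather than inside the folds, without the outcome in the model, changed the RMSE by 0 to -1% at n = 44-55 and by about 0% at n = 200. With every child's outcome in the model, the change at n = 44-55 was about -4% with 10% missing (8.85 against 9.23 at n = 44) and about -12% with 30% missing (8.47 against 9.67). At n = 200 it was -3% and -9%.

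**The case against.** The strongest reply is that most of this rests on silence. The plan does not say that folds were shared, that tuning was un-nested or that imputation preceded splitting. It reports no RMSE that could be shown to be wrong. A reader might infer from the order of the sentences that imputation was done outside the folds. Order is the only evidence for that, and even if true it matters little unless the outcome was in the imputation model. This part of the reply stands. On tuning it stands less well: one optimisation per model, followed by a cross-validation on the same children, is the natural reading, and new folds would not cure it.

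The sample size is a second fair objection. All 55 recruits are described as undergoing SEMLS and must have had no prior surgery, yet Table 1 has a yes/no SEMLS variable and a list of prior surgical treatments. The BART data may therefore extend beyond the 55, and with more children the optimism shrinks. The stand-ins are also not BART, and the grid is invented. Both points stand and limit the figures to orders of magnitude.

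Third, the RMSE is peripheral. The plan uses BART for causal effects and reads individual variables from ALE plots, and it ties no decision to the RMSE. This stands.

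A reader might also infer that the optimism makes a worthless model look useful. In simulation B with no signal, the cross-validated R-squared was -0.022 tuned and -0.105 nested, negative either way. With a weak signal the sign did change (0.038 against -0.067), but the plan does not say that it reports a cross-validated R-squared.

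**Conclusion.** The point holds in a limited form. As written, the out-of-sample label is not secured, because tuning and error estimation both use ten-fold cross-validation on the same children, with neither nesting nor a held-out set described. On that reading the RMSE is expected to be modestly optimistic: roughly 1-6% at n = 44-55 and about 1% at n = 200. These figures assume tuning on the full sample, 12-13 predictors, an 18-point grid for the kernel results, and proxies for BART. They are not estimates for this study.

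Three stronger readings are not supported. The documents do not show that the reported error *is* too small, since they report none. They do not show that imputation was done outside the folds. Nor do they give grounds to doubt the causal-effect or ALE estimates on this account, since nesting the RMSE would leave those unchanged.

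**What to change.** Obtain the RMSE by nested cross-validation. Use ten outer folds and, within each outer training set, refit the imputation model and choose the hyperparameters by an inner ten-fold loop. Then predict the held-out children, imputing their missing baseline impairments without using their outcomes. State the number of children in each BART model, the grid, the seeds, the number of imputations and whether the outcome enters the imputation model.

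If this is not done, relabel the figure as tuning-sample cross-validation error and drop the out-of-sample description.

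The cost is a few lines of code and about ten times the computing. With 18 settings, for example, there are 10 x (18 x 10) + 10 = 1,810 model fits instead of 18 x 10 + 10 = 190, a ratio of 9.5. The RMSE is likely to be slightly less favourable. Comparing models with and without DMC, or repeating the splits, would answer other questions and is not needed here.

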These results motivate our proposed research to use synergies as a framework to quantify altered neuromuscular control in CP and inform treatment planning. There are several important knowledge gaps that need to be addressed to determine the clinical utility of synergy analyses. First, we need to determine if an individual's synergies predict treatment outcomes and provide additional insight beyond traditional tools of clinical motion analysis. Second, we need to establish the adaptability of synergies. EMG is typically only collected before treatment in clinical motion analysis and we do not know if or how neuromuscular control changes after treatment. If synergies can change, new treatment strategies such as biofeedback training may be able to target altered synergies and improve movement. If synergies do not change, we can use an individual's synergies to predict responses to different treatments and identify their "best" possible gait pattern given their neurologic capacity. Finally, from a theoretical perspective, we need to further develop our understanding of the contribution of altered synergies to impaired movement in CP. We developed a new algorithm in OpenSim, an open-source platform for musculoskeletal modeling, which allows users to specify and test different control strategies. We will use this platform to create patient-specific simulations and evaluate how changes in synergies influence muscle recruitment, movement, and energy costs of walking.

The long-term goals of the proposed research are to improve movement and quality of life for individuals with CP. This proposal will determine if quantifying altered neuromuscular control with synergy analysis and musculoskeletal simulation can provide clinicians with new tools to optimize treatment and improve walking ability. Our specific aims are to:

Aim 1: Determine if pre-operative synergies predict outcomes at 12 months after orthopaedic surgery. We will recruit 55 individuals with diplegic cerebral palsy (CP) who are undergoing single-event multi-level orthopaedic surgery (SEMLS) at Gillette for standard of care. Each individual will receive gait analysis including EMG to evaluate synergies before and after surgery, which is part of standard of care. We hypothesize that individuals with more complex synergies (i.e., synergies similar to unimpaired individuals) will have greater improvements in walking kinematics, energy costs, and quality of life 12 months after orthopaedic surgery.

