Aim 2: Evaluate stability of synergies with respect to time and treatment. With the same participants as Aim 1, we will compare synergies during gait between two visits before surgery and 6 and 12 months after surgery. This investigation will determine whether synergies are repeatable between days in CP and whether synergies adapt or change in response to surgical changes to the musculoskeletal system.

Human Subjects Involvement, Characteristics, and Design

Aims 1 and 2 will use the same set of subjects to evaluate if synergies predict outcomes after SEMLS (Aim 1) and if synergies change after surgery (Aim 2). We will recruit 55 individuals with CP who have been recommended for surgical treatment at Gillette Children's Specialty Healthcare over three years. Our inclusion criteria for Aims 1 and 2 are: age > 6, diagnosis of spastic diplegic cerebral palsy, GMFCS Levels I-III, absence of dystonia/ataxia/athetosis, no prior surgical procedures, no pharmacological spasticity treatments (e.g. botulinum toxin, baclofen, etc.) within 3 months prior to first gait analysis, capacity to follow instructions and provide informed assent, ability to walk across 30 ft. walkway at least 10 times, absence of acute or chronic pain in lower-extremities, and no current pharmacological agents that impact neuromuscular control. Subjects will be recruited who are being evaluated for SEMLS surgery and includes one or more of the following procedures: femoral and tibial derotation osteotomies, surgical lengthening of the gastrocnemius, psoas, hamstrings and adductors, bone and soft tissue alignment of the foot, botulinum toxin injection, distal femoral extension osteotomy, and patellar tendon advancement. Subjects will not be excluded on the basis of ethnic background, race, sex, or socioeconomic factors.

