To assess the relative effects of individual variables from BART, we used accumulated local effect (ALE) analysis¹². The ALE analysis is similar to a partial dependence plot, but the averaging is done locally to avoid including observations that are unlikely to ever be realized (e.g., someone walking three standard deviations slower than average but with a normal cadence). The ALE plots illustrate the impact of each variable over the range of values for that variable, conditioned on the other covariates in the model. Thus, ALE plots can be useful for examining nonlinear effects identified by BART. For example, the ALE plot can highlight nonlinear effects such as when a variable impacts GDI with a deviation from average (i.e., a U-shaped plot) or when a variable only impacts GDI above or below a certain cut-off (i.e., a step function or discontinuity).

Table 1: Variable definitions

Variable	Description
GDI	Overall measure of the deviation in an individual's kinematics compared to nondisabled peers scaled such that mean(sd) over the nondisabled population is 100(10) ¹³ . Kinematics were evaluated using marker-based motion analysis and a modified plug-in-gait marker set.
SEMLS	Binary variable indicating whether or not child had single-event multi-level orthopedic surgery, defined as a surgery with two or more orthopedic surgeries on at least one leg.
Hx	Binary list of prior surgical treatments.
Age	Years from birth defined as days/365.25
Impairments	Spasticity: Mean modified Ashworth score across plantarflexors, hamstrings, hip adductors, and rectus femoris.
	Strength: Mean manual muscle strength score across hip flexors/extensors, knee flexors/extensors, and ankle dorsiflexors/plantarflexors where 1 is defined as a 'visible or palpable contraction' and 5 is defined as 'full range of motion against gravity'.
	Static Motor Control (SMC): Mean static motor control score across hip abduction, hip flexion, hip extension, knee extension, and ankle plantarflexion where 0 is very little or no control of single joint movement, 1 is impaired voluntary movement at a single joint, and 2 is good voluntary movement at a joint.
	Dynamic Motor Control (DMC): Measure of the complexity of muscle activity during gait evaluated from synergy analysis of EMG data. Complexity is evaluated as the total variance accounted for by one synergy of EMG data during CGA and compared to nondisabled peers scaled such that mean(sd) over the nondisabled population is 100(10) ^{14,15} .

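### The DMC effect is read from an ALE curve with no stated interval, and no BART model with DMC is compared with one without it, so the plan does not quantify what synergies add.

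*Combined protocol and SAP*

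**What the plan says.** The Background of the protocol names as its first knowledge gap whether an individual's "synergies predict treatment outcomes and provide additional insight beyond traditional tools of clinical motion analysis". Aim 1 takes up the prediction part. The STATISTICAL ANALYSIS section assigns it to causal modelling and BART, to "evaluate whether pre-operative synergy complexity and structure are associated with changes in GDI after SEMLS at 12 months post-op".

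That section then describes three outputs:

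- **Pseudo-R²**, defined as 1 − SSE/SST, and a **10-fold RMSE**: "for each BART model and used k-fold cross-validation". Only the RMSE is called out-of-sample, so the pseudo-R² reads as in-sample.
- **ALE curves** for single variables: "To assess the relative effects of individual variables from BART, we used accumulated local effect (ALE) analysis". On what they show: "The ALE plots illustrate the impact of each variable over the range of values for that variable, conditioned on the other covariates in the model".

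The models are built "using the adjustment sets identified by the DAG". For the SEMLS effect the set is Age, baseline GDI and baseline impairment. For the impairment effect, "The minimal sufficient adjustments sets were Age and Hx for" change in GDI. Table 1 lists DMC as one of the impairments.

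**The concern.** Asking what synergies add to existing tools is an incremental question. It needs a comparison with what baseline GDI and the physical-exam measures predict on their own. Pseudo-R² and RMSE describe all predictors together, so a good value could come entirely from baseline GDI. The ALE curve is specific to DMC, but the SAP attaches no interval, band, test or numerical summary to it. It also does not say how uncertainty from the MICE imputation reaches the curve.

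At small N, a modest rise in such a curve may be a real effect, noise, or a share of the effect of a correlated impairment such as static motor control (SMC). A report could credit DMC for a chance swing or dismiss a real modest effect. In neither case would it give a figure for what DMC adds.

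**Working it through.** **1. Question against output**

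| Question | Output in the SAP | What is missing |
|---|---|---|
| Is DMC associated with change in GDI? | ALE curve, adjusted for the other covariates | Any statement of uncertainty |
| Does DMC add to traditional tools? | Pseudo-R² and RMSE of whole models | A comparison with and without DMC |

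No nested comparison, change in R² or RMSE, or permutation of DMC appears anywhere in the document.

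**2. The plan's own sample size.** Inputs from the STATISTICAL ANALYSIS section: half an SD, 90% power, alpha 0.05 (taken as two-sided), 20% drop-out. For a paired t-test with n = 44, the noncentrality is 0.5 × √44 = 3.317, the critical t on 43 df is 2.017 and the power is 0.900. Then 44 / 0.80 = 55, which matches exactly. The SAP says that this figure rests on Aim 2. It says nothing about precision for Aim 1.

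**3. Linear benchmark for DMC.** This is a simpler stand-in for BART.

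- Predictors: Age, baseline GDI and ten impairment measures from Table 1 (spasticity, strength, SMC, DMC, two torsional, four contracture), 12 in all.
- Assumed: N = 44, outcome variance 1, baseline GDI slope −0.5, DMC slope b, uncorrelated predictors.
- Residual variance = 1 − 0.25 − b²; f² = b² / residual variance; df = 44 − 13 = 31; critical t = 2.040; noncentrality = √(f² × m), with m = 31 to 32.

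| b | f² | Noncentrality | Power, N = 44 | Power, N = 100 |
|---|---|---|---|---|
| 0.30 | 0.09 / 0.66 = 0.136 | 2.06-2.09 | 51-53% | 93% |
| 0.15 | 0.0225 / 0.7275 = 0.031 | 0.98-0.99 | 16% | 37% |

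The N = 100 column uses df = 87. If the SD of change in GDI is 8 to 12 points (assumed), b = 0.3 means 0.3 × 0.5 × 8 = 1.2 to 0.3 × 0.5 × 12 = 1.8 points per half SD of DMC. For b = 0.15 it means 0.6 to 0.9 points.

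**4. How variable the added-value figure would be.** Linear regression was simulated with N = 44, 11 other predictors, SD of change in GDI 10 and R² of the other predictors 0.30 (all assumed). The fall in 10-fold RMSE from adding DMC, with its 95% range over simulated trials, was:

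- partial R² 0: −0.19 (−0.77 to 0.56)
- partial R² 0.10: 0.33 (−0.58 to 1.91)
- partial R² 0.20: 0.91 (−0.33 to 2.88)

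The range includes zero even at 0.20.

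**5. How often an unbanded curve swings.** This is illustrative only. BART (50 trees, one shrinkage parameter tuned by cross-validation) was simulated with the Age + Hx set and all ten impairments. At N = 44 Hx drops out, because the inclusion criteria require "no prior surgical procedures". At N = 100 two Hx indicators were included. The share of datasets with a DMC ALE range above 0.2 SD was:

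| Truth | N = 44 | N = 100 |
|---|---|---|
| No DMC effect | 9% | 4% |
| No DMC effect, DMC correlated 0.5 with an SMC of slope 0.3 | 25% | 21% |
| DMC slope 0.15 | 21% | 26% |
| DMC slope 0.30 | 48% | 74% |

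With 90 to 155 datasets per cell, Monte Carlo error is up to about 5 points. The second and third rows are not separated at either N.

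**The case against.** The strongest reply is that the ALE curve is itself an adjusted DMC estimate. That is correct. A reader might infer that the plan yields no DMC-specific result at all, but the SAP states that the curves are conditioned on the other covariates. Only the uncertainty and the incremental figure are missing.

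Second, the added-value question stands in the Background, while Aim 1 asks about prediction and the SAP targets association and total causal effects. The SAP gives an adjustment set for the effect of impairment on baseline GDI, so it treats baseline GDI as affected by impairment. A comparison that conditions on baseline GDI therefore answers a different question from the total effect. This stands, and the comparison must be labelled accordingly. It does not excuse the missing interval, which matters for the association question too.

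Third, a reader might infer that the source model of the DMC curve is undetermined. The natural reading is the Age + Hx model, since DMC is an impairment; what is missing is mostly a label. The model matters for the illustration: with baseline GDI included, null swings above 0.2 SD were more frequent (30% / 20% at N = 44 / 100), but that is not the set named for impairments.

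Fourth, the assumed slopes are small beside the SAP's preliminary figure of 5 GDI points per half SD of DMC. The SAP does not say whether that figure was adjusted or refers to change in GDI. Still, a large effect would probably be visible without a band. BART also produces a posterior from which bands could be drawn, but the plan does not commit to drawing them.

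**Conclusion.** The point holds as a gap in reporting and analysis. The plan gives no uncertainty for the DMC effect and no estimate of DMC's incremental predictive value, and the sample size was not set for either. That follows from the text alone.

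The size of the consequence rests on assumptions. With N = 44, 12 uncorrelated predictors and a linear model, power is about 51-53% at a slope of 0.3 SD and 16% at 0.15 SD, so modest effects need an interval to be read. The modelled N is not stated. Table 1 defines SEMLS as a yes/no variable, which suggests that the data may extend beyond the operated cohort; at N = 100 the benchmark rises to 93% and 37%.

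The document does not support the inference that the curve is uninformative. The simulated swing rates depend on assumed slopes and correlations and carry appreciable Monte Carlo error. They show only that an unbanded modest swing is ambiguous.

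**What to change.** 1. Draw the DMC ALE curve from the Age + Hx impairment model with 95% posterior bands combined over the imputations. Label it as coming from the total-effect analysis of baseline impairment that the SAP names.
2. As a separate analysis, labelled incremental prediction and not a causal effect, report the paired difference in out-of-fold RMSE, with an interval, between BART models with and without DMC. Both should contain Age, baseline GDI and the other Table 1 impairments, and use the same folds, with tuning and imputation inside each training fold.
3. State N for each model.

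Out-of-fold R² is optional, since it largely re-expresses the RMSE already planned. A permutation reference for DMC is also optional.

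The cost is extra code and computing time, with no new data. The yield is limited near N = 44. In the illustrative BART simulation with baseline GDI in the model and a slope of 0.3, the 95% interval for the rise of the ALE curve excluded zero in 17% of datasets, and a simple paired interval for the prediction gain lay wholly above zero in 11%. A null result must therefore be reported with its interval as inconclusive, not as evidence that synergies add nothing.
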